We anticipate that all patients will see minimal improvement in symptoms during the baseline period between the clinical evaluation and baseline pre-tx, and significant improvement from pret-tx to mid-tx and post-tx. In addition, we hypothesize that patients treated in the either PCET condition will demonstrate greater reductions in anxiety symptoms and impairment, as well as require fewer total treatment sessions, compared to patients in traditional CBT. To test this hypothesis, repeated-measures analyses of variance (which controls for baseline symptom severity) will be conducted to assess the change that occurs over time and between conditions. Because treatment changes after mid-treatment for some conditions, but not others, we will examine the changes at mid-treatment and post-treatment separately. The primary outcome variable will be change in symptom severity on a continuous variable as measured by the IE administered CGI-S. Secondary outcomes will be anxiety symptoms measured through parentreport (SCAS-P), child-report (SCAS-C), and clinician report (PARS). Dichotomous measures of improvement used in the literature will include receiving a score of 1 or 2 on the CGI-I, reduction on the PARS of 35% (response) and 50% (remission). Tertiary outcome variables will be impairment measured through the CSDS. Efficiency will be measured at the group level by number of treatment hours (included phone contacts) and symptom change effect size per hour of intervention. Number of dropouts vs. completers will be examined. Finally, we will examine treatment acceptability through the rate of drop-out and ratings of alliance. All statistical analyses will be conducted using intent-to-treat and completer analyses. Because patients that agree to each randomization option may differ in unmeasured ways, comparator analyses will be run in two ways. First, to avoid biasing the results by combining incompatible groups, we will include patients in comparisons only if they agreed to be randomized to each option (i.e., only patients that agreed to the possibility of being randomized to CBT will be included in the comparison between PCET-I and CBT). Second, to maximize power, we include all patients with randomization agreement as between subject variables. Exploratory analyses will include examining the relation to randomization choices and the moderating effects on outcome of diagnosis (OCD vs. anxiety disorder), symptom severity, age, medication use, etc.

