Power Statement: Based on the mean mid-tx CGI-S scores from the pilot study (PCET= 2.33, sd= .8; CBT = 3.17, sd =.8) and 14 patients are required per group to achieve 80% power to detect a difference between two groups at a p value of .05. Thus, the current proposed sample size of 20 participants be treatment conditions should be sufficient.

In regard to acceptability, we will assess the acceptability of each treatment to patients and their families. A between-groups analysis of variance will be conducted to assess for differences in the alliance and satisfaction of each treatment at posttreatment. Further, we will also conduct between-group mean comparisons of the number of drop outs.

Sample representativeness will be examined through group differences between patients that participated and those that declined through t-tests and chi-square analyses of symptom and demographic data collected at the clinical assessment.

Remuneration

Patients can earn up to \$50 for participation: up to \$25 for completing research assessments (\$5 for pre-treatment assessment and \$10 for each of the mid- and post-treatment assessments); up to \$25 for randomization: \$15 if they agree to the possibility of being randomized to one comparator and additional \$10 for agreeing to be randomized to the second comparator. All remuneration will be paid when the participant completes the study, and may be pro-rated based on completion of assessments. Patient remuneration will be payed from [name] research funds.

7. Possible Discomforts and Risks:

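### CGI-S change is named as the primary outcome, but the plan does not say which arm comparison, time point, population or analysis set decides the trial, and it has no multiplicity rule

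*Combined protocol and SAP*

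**What the plan says.** The Statistical Plan (section 6) makes interviewer-rated CGI-S change the single primary outcome variable. Four features then multiply the ways of testing it.

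- **Arm comparisons.** Section 5 asks for PCET-I v CBT (Aim 2) and for PCET-5day against both PCET-I and CBT (Aim 4), three in all. The Statistical Plan's hypothesis predicts a direction only for the two PCET conditions against CBT.
- **Time points.** "we will examine the changes at mid-treatment and post-treatment separately". The reason given is that treatment changes after mid-treatment in some conditions.
- **Populations.** "All statistical analyses will be conducted using intent-to-treat and completer analyses".
- **Analysis sets.** "comparator analyses will be run in two ways": first, only patients who agreed to the option being compared, to avoid bias; second, all patients, with randomisation agreement entered as a between-subject variable, to gain power.

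The only significance level in the documents is in the Power Statement. It works from pilot mid-treatment CGI-S means for PCET and CBT and states that "14 patients are required per group to achieve 80% power" for a two-group difference "at a p value of .05". It does not say that this comparison is the decisive one.

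**The concern.** Naming a primary variable does not name a primary test. With three comparisons, two times, two populations and two analysis sets there are 3 x 2 x 2 x 2 = 24 possible CGI-S results. Nothing says which one settles the question, or what follows if they disagree. Followed as written, the plan would let success be claimed from any of them.

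The versions also answer different questions. The CBT arm does not discuss exposure in its first six sessions and receives it afterwards, so mid-treatment compares exposure with anxiety management, while week 14 compares earlier with later exposure. The first analysis set is limited to families who accepted the randomisation in question. The second also includes families not randomised to that comparison, some of whom took PCET by preference. The Abstract promises a more definitive test of efficacy, and that needs one criterion fixed in advance.

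**Working it through.** **1. The plan's own figure.** Inputs from the Power Statement: means 2.33 and 3.17, SD 0.8, 80% power, level .05. The level is taken as two-sided, which the documents do not state.

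Difference = 3.17 - 2.33 = 0.84; d = 0.84/0.8 = 1.05.

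n per group = 2(1.960 + 0.842)²/1.05² = 14.2.

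This agrees with the stated 14 apart from rounding; an exact t-test needs 15.3, so 16. The plan's one calculation is therefore for one contrast at one time.

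**2. Upper guide, treating tests as independent.** The chance of at least one false positive in k tests is 1 - 0.95^k:

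- k = 4 (two contrasts, two times): 18.5%
- k = 6 (three contrasts, two times): 26.5%
- k = 24: 70.8%

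The tests share patients and are positively correlated, so these figures overstate the risk.

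**3. Simulation under no effect.** For two arms and two occasions, the condition-by-time test in a repeated-measures ANOVA is equivalent to a t-test on change, so t-tests on normal change scores were used at two-sided .05. The correlation between mid- and post-treatment change is not in the documents and was varied from .3 to .9. Both 20 per arm (Power Statement) and 40 per arm (Participants) were run, with 200,000 simulated trials per setting:

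| Tests counted | r = .3 | r = .5 | r = .7 | r = .9 |
|---|---|---|---|---|
| PCET-I v CBT, two times | 9% | 9% | 8-9% | 7% |
| Both contrasts with CBT, two times | 17% | 16% | 15% | 13% |
| All three contrasts, two times | 22% | 21% | 20% | 17% |
| Three-arm omnibus ANOVA, two times | 9-10% | 9% | 8-9% | 7% |

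The choice of 20 or 40 per arm moves these by less than half a percentage point.

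**4. Adding the completer and all-patients versions.** This needs further assumptions: dropout 5-20%, share in the agreed subset 40-95%, and no selection effect from agreeing. With 20,000 trials per setting, the chance was 17-36% over the 16 versions of the two CBT contrasts and 23-45% over all 24. Those runs thin every arm alike, although everyone randomised to CBT must have agreed to it. Keeping the CBT arm whole in four of the settings gave 17-34% and 22-42%. These ranges are indicative only.

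**5. After naming one test.** The false-positive chance is 5%. At d = 1.05 a two-sided t-test has about 90% power with 20 per group and above 99% with 40. If fewer families are in the agreed subset, power falls: 76% with 14 per group and 60% with 10.

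**The case against.** The strongest reply is that the plan gives more direction than a count of 24 suggests. The Power Statement is built on mid-treatment CGI-S for PCET v CBT. The separate time points are explained. The agreed-to-randomisation analysis comes first and is justified as avoiding bias. A sympathetic reader would find the main test there. That stands as a reading, but the plan never states it, and the Power Statement says nothing about population or analysis set.

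The size is also open to challenge. PCET-5day v PCET-I has no predicted winner, so counting it as a route to success is debatable. Without it the core figure is 13-17%. If only false positives favouring PCET over CBT are counted, it is 6-9%, against 2.5% for a single two-sided test. The named method is an ANOVA across conditions. If a three-arm test at each time were the test, the figure would be 7-10%. The plan does not require that test before the pairwise comparisons, and its own example, PCET-I v CBT, is pairwise.

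A reader might infer that 24 tests will each be declared at .05, with a false-positive chance of 20% or more as a fixed property of the trial. The documents do not support that. The .05 appears only in the Power Statement, the completer and all-patients versions may be meant as sensitivity analyses, and the rate depends on which tests count. Nor does the plan ignore the mixing of families in the all-patients analysis: it enters randomisation agreement as a factor. That may not remove every difference between the groups, but it is a stated adjustment.

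**Conclusion.** The point holds in a limited form. The plan leaves the decisive comparison, time, population and analysis set open and gives no order or multiplicity rule, which is more than a missing detail because the choice could be made after the results are seen. If each test uses .05, the chance of at least one false positive is about 13-17% for the hypothesised contrasts and about 17-22% for all three, each over two times. It is higher if the other versions also count, and 7-10% under an omnibus reading. So 20% is one reading and not the error rate of the trial, though every reading exceeds 5%.

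The figures rest on normal change scores, a two-sided level inferred from the Power Statement and an assumed mid/post correlation of .3 to .9. The absence of a named decisive test rests on the text alone. Data collection is unaffected. The plan should be amended before the outcome data are analysed.

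**What to change.** Add a paragraph to the Statistical Plan that does three things.

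1. Declare one primary test: CGI-S change, PCET-I v CBT, at mid-treatment, by intent-to-treat, in families who agreed to possible randomisation to CBT, at two-sided .05. This is the comparison the sample size was calculated for, in the analysis set that the plan itself uses to avoid bias.
2. Label the completer analyses and the all-patients analyses as supportive. For the latter, say that they adjust for randomisation agreement but include families not randomised to the comparison.
3. Make the other contrasts and week 14 secondary, either in an order stated in advance or with a stated adjustment. The order is the sponsor's choice. Week 14 needs a note that the CBT arm may by then have received exposure.

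**Cost.** No extra assessments are needed and the primary test carries no alpha penalty. It does use only the agreed-to-CBT subset, so the roughly 90% power requires about 20 such families per group under the pilot assumptions. The plan should state the expected size of that subset and settle whether the target is 20 or 40 per arm. Versions left outside the sequence lose confirmatory status. Keeping all six contrast-by-time tests co-primary with Bonferroni (.05/6 = .0083 each) would instead give about 70% power per test at 20 per group, or 97% at 40, assuming the pilot effect.

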Following the consent process, families who agreed to be randomized to a comparison treatment participate will be assigned to a treatment condition through random assignment. Families that did not agree to randomization will be scheduled in PCET (individual or intensive group depending on preference). The families will then be scheduled to begin therapy at the earliest date available. All enrolled families will complete the pre-treatment research assessment the day they begin treatment. The families will then begin treatment.

The mid-treatment evaluation will be completed after the sixth session for patients in the individual treatment conditions and six weeks after the start of treatment in the intensive group condition. After the mid-treatment assessment families in all conditions can receive any type of therapy interventions with their study therapist. The final assessment will be completed 14 weeks after the first session. All study assessments and individual treatment sessions will be recorded, unless participants opt-out of recording, to examine therapist fidelity. Families will record progress each week using a study form which will be gathered by therapists during visits and by therapists (or other study staff) via electronic message or telephone calls in the absence of inperson appointments.

Tests/Measures Administered

Table 2 Summarizes when study measures are completed, by whom and whether they are administered as part of clinical practice or as part of the research study.

Interviewer--administered measures: The interviewer measures will be administered by the practicing clinician at initial clinical interviewer and by study staff blind to the treatment condition at pre-, mid-, and post-tx.

(1) The MINI-Kids (Sheehan et al., 2010). This is a clinician-administered, structured interview that is currently administered as part of the PADC standard evaluation. Administered at clinical interview only.

(2) Pediatric Anxiety Rating Scale (*PARS; (Group, 2002).* The PARS is an interviewer administered scale consisting of five items assessing anxiety severity, frequency, distress, avoidance, and interference. The PARS has good psychometric properties (Group, 2002) and has been used as the primary continuous outcome measure in previous treatment studies (e.g., (Walkup et al., 2008).

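### Intent-to-treat is promised with no rule for missing scores, and the named ANOVA by default drops randomised families who lack either score of the pair being compared

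*Combined protocol and SAP*

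**What the plan says.** All of this is in the combined protocol and SAP, section 6 (Research Plan).

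- Statistical Plan, analysis sets: "All statistical analyses will be conducted using intent-to-treat and completer analyses". Neither set is defined.
- Statistical Plan, method: "repeated-measures analyses of variance (which controls for baseline symptom severity) will be conducted to assess the change that occurs over time and between conditions".
- Statistical Plan, time points: because treatment changes after mid-treatment in some arms, "we will examine the changes at mid-treatment and post-treatment separately".
- Statistical Plan, primary outcome: "The primary outcome variable will be change in symptom severity on a continuous variable as measured by the IE administered CGI-S".
- Statistical Plan, dropout: "Number of dropouts vs. completers will be examined". The acceptability paragraph after the Power Statement also compares dropout numbers between groups. No section mentions imputation, carrying scores forward, a mixed model or any other way of handling a missing score.
- Procedures, timing: "The mid-treatment evaluation will be completed after the sixth session for patients in the individual treatment conditions". In the intensive group it falls six weeks after the start. The final assessment is set by the calendar, at week 14, whether or not therapy continues.
- Procedures, weekly ratings: "Families will record progress each week using a study form which will be gathered by therapists during visits", and by message or telephone when there is no in-person visit. The Statistical Plan gives these ratings no role.

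**The concern.** With two occasions, the group-by-time test in a repeated-measures ANOVA is the same as a t-test on the change score. A child without both scores has no change score and leaves the test. Because mid- and post-treatment are analysed apart, a mid-treatment CGI-S already on file does nothing for a family with no week-14 score.

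Nothing in the plan therefore keeps such a family in the result labelled intent-to-treat. Two things are at stake. The week-14 comparison could be biased if the families who go missing differ between arms in how well they were doing. And agreement between the intent-to-treat and completer results could be read as robustness when it partly reflects the same families being used twice. With no rule written down, the choice could also be made after the data are seen.

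**Working it through.** **1. The plan's own figure.** The Power Statement gives mid-treatment CGI-S means of 2.33 and 3.17, SD 0.8, p = .05 and 80% power. With a two-sided test (sidedness is not stated):

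n per group = 2 × [0.8 × (1.960 + 0.842) / 0.84]² = 14.24, so 15; the t-test version gives 15.26, so 16.

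The stated 14 is reproduced to within 2 patients. It includes no allowance for dropout.

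**2. Does the method drop families?** In a constructed data set of 40 children with 6 follow-up scores missing, the group-by-time test used 34 of 40.

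**3. Precision.** The documents give no dropout rate, so 15-30% is assumed. Retained per arm = n × (1 − loss).

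- 20 per arm (Power Statement): 20 × 0.85 = 17; 20 × 0.70 = 14.
- 40 per arm (Participants): 40 × 0.85 = 34; 40 × 0.70 = 28.

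For the pilot difference (0.84, SD 0.8), t-test power at 20 per arm is 89.9% with no loss and 76.2% at 30% loss. At 40 per arm it stays at 94.5% or higher even at 40% loss.

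**4. Bias at week 14.** Only the SD and the mid-treatment means come from the documents. Assumed inputs:

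- baseline mean 4.5 in both arms; week-14 means 2.0 (PCET) and 2.6 (CBT), so the true difference is 0.60;
- jointly normal scores, with two sets of correlations;
- withdrawal after mid-treatment that depends on the mid-treatment score (logistic, slope 1 per SD), with 15% or 30% lost.

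Let s be the average standardised mid-treatment score of the retained families, relative to their whole arm. Then

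complete-pair difference = 0.60 + 0.8 × (r[mid,post] − r[pre,mid]) × (s[CBT] − s[PCET]).

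Under this withdrawal model s is about ±0.13 at 15% loss and ±0.25 at 30%. If low (well) PCET scorers and high (unwell) CBT scorers leave, s[CBT] − s[PCET] is −0.26 or −0.50. In the reverse case it is +0.26 or +0.50. With the same pattern in both arms it is 0.

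| Correlations pre-mid / pre-post / mid-post | Loss | Well PCET and unwell CBT leave | Unwell PCET and well CBT leave | Same pattern in both arms |
|---|---|---|---|---|
| .5 / .4 / .6 | 15% | 0.60 − 0.8 × 0.1 × 0.26 = 0.58 | 0.62 | 0.60 |
| .5 / .4 / .6 | 30% | 0.60 − 0.8 × 0.1 × 0.50 = 0.56 | 0.64 | 0.60 |
| .3 / .2 / .7 | 15% | 0.60 − 0.8 × 0.4 × 0.26 = 0.52 | 0.68 | 0.60 |
| .3 / .2 / .7 | 30% | 0.60 − 0.8 × 0.4 × 0.50 = 0.44 | 0.76 | 0.60 |

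Simulation with large arms agrees to about 0.01 (lowest value 0.43 to 0.44). An estimate that also uses the mid-treatment score of families without a week-14 score returns about 0.60 in every row. It does so because withdrawal was made to depend only on that observed score.

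**The case against.** The strongest reply is that the plan is silent; it does not say complete pairs will be used. Naming intent-to-treat beside completer analyses suggests that some distinct rule was intended, and imputed or carried-forward scores can be fed into an ANOVA. That is fair. Deletion is what the method does by default, not something the plan declares.

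A reader might go further and infer that the intent-to-treat analysis is simply a second completer analysis. The documents do not support that. Completer is undefined. The week-14 assessment is fixed by the calendar, consists of questionnaires and a short phone or video call, and is paid for. If completer means finishing therapy, a family that stops sessions but gives a week-14 score belongs to the intent-to-treat set and not to the completer set, so the two results could differ.

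A reader might also infer that the effect will be understated because PCET families improve and leave. The plan predicts fewer sessions with PCET, which is its efficiency outcome and not study withdrawal. The other half of that story, unwell CBT families leaving after mid-treatment, is weakened because the CBT arm moves to exposure after session 6 with no cap on sessions. The reverse pattern overstates the effect, so the direction cannot be known in advance.

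Finally, the precision loss matters mainly at 20 per arm; the Participants section plans 40.

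What the reply does not answer is that no stated mechanism keeps a family without a follow-up score in the intent-to-treat result.

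**Conclusion.** The concern holds in this form: intent-to-treat is promised, no missing-score rule is given, and the one named method by default drops any family lacking either score. The intent-to-treat result may therefore differ little from the completer result; it is not shown that it must.

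Under the assumed inputs and 15-30% loss, the week-14 difference ranges from about 0.44 to 0.76 against a true 0.60 when withdrawal follows opposite patterns in the two arms. With correlations of .5/.4/.6 the error is at most 0.04; with .3/.2/.7 it reaches 0.16. With the same pattern in both arms there is no bias, and the cost is precision alone. These are illustrations, because the documents give no withdrawal rates, correlations or week-14 means. The plan should be changed, chiefly because a better method is available at little cost.

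**What to change.** - For the intent-to-treat analysis, replace the separate ANOVAs with one likelihood-based mixed model for repeated measures, fitted to all available pre, mid and post CGI-S scores with families as randomised. Fit it within each comparison's set of families who agreed to that randomisation option, as the Statistical Plan already requires for its first comparison. Read the arm-by-time contrasts separately at mid and post, which respects the plan's reason for separating them.
- Define completer, stating whether it means finishing therapy or providing scores. Keep the complete-pair ANOVA and label it the completer analysis.
- State the missing-at-random assumption and add one sensitivity analysis for scores not missing at random. The weekly 0-10 ratings may optionally serve as auxiliary variables in imputation.

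The cost is plan wording and slightly more analysis work, with no new data. The limit is that the model rests on missingness being explained by observed scores, and it recovers little for families with only a baseline score. In the individual arms that includes families who leave before session 6, since their mid-treatment assessment is tied to that session.

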Patients will be excluded from the study if they meet any of the following criteria: (a) history of and/or current psychosis, autism, bipolar disorder, or current suicidality, or eating disorder as assessed during the initial clinical interview and all available clinical information; (b) current positive diagnosis in the child's caregiver of mental retardation, psychosis, or other psychiatric disorders or conditions that would limit his/her ability to understand CBT and follow-through with treatment directives (based on clinical interview); (c) secondary diagnosis of oppositional defiant disorder or major depression of sufficient severity to prevent anxiety treatment, (d) severity of symptoms that warrant higher level of care (i.e. intensive, residential, IOP, inpatient), (e) family is unable to attend weekly sessions (i.e. geographical or scheduling barriers), of (f) history of good quality exposure or CBT.

Procedures

See Figure 1. Participants who have contacted or been referred to the PADC for evaluation and treatment of an anxiety disorder will complete the standard clinical intake procedure for the PADC. Families whose children meet the inclusion criteria will be provided a description of the study procedures and asked which aspects of the study they are willing to participate in. All families will be asked to complete three research assessments (pre-, mid-, and post-treatment) consisting of completing questionnaires and a short phone or video call. Families will be provided with a description of the three treatment options and informed that PCET is the default treatment option. They will then be asked if they are willing to be randomized to a treatment from two or three of the options. Randomization will be accomplished through a random number generator and will allow for a comparison of the relative effectiveness of each treatment by

controlling for other variables that might impact treatment outcome. The individual PCET is currently the standard treatment offered through the PADC and patients not interested in this treatment are not eligible for the study. When families are interested and eligible in participating in the clinical trial, the therapist or a study coordinator will obtain written consent and assent.

Families who decline to participate will have the PADC.

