The design of the current study is intended to maximize participation through providing options for participation. First, families have the option to provide data without submitting to randomization of treatment condition. The inclusion of families that are willing to complete the research assessments even though they are unwilling to be randomized to a comparison condition is intended to minimize the number of families that decline to participate. As such, this option increases the likelihood that participants accurately represent the population of patients seen in the PADC. Because these patients will receive PCET, it increases the number of patients receiving the intervention of most interest. In addition, because these families will participate in a baseline period of no treatment before attending the first treatment session, symptom improvement with treatment can be compared to that without treatment. Similarly, by allowing families to select the chance to be randomized to one or both CBT or PCET-5day as a comparator, we intend to maximize the number of patients for whom there is an acceptable option.

Personnel

Therapy will be provided by the staff of the PADC and psychology fellows that have completed the PADC rotation. The PI has trained and supervised all therapists and will provide additional training in the traditional CBT protocol. Assessments will be conducted by the study staff, blind to condition. The PI will provide training in the assessments.

Statistical Plan

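### The first comparator analysis pools families randomised from two-option and three-option sets with no option-set term; adding one gains a little precision and guards against bias if allocation ratios differ

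*Combined protocol and SAP*

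**What the plan says.** Under 6. Research Plan, Procedures, families are asked "if they are willing to be randomized to a treatment from two or three of the options". PCET-I is the clinic's standard treatment, and "patients not interested in this treatment are not eligible for the study", so it belongs to every option set. Design Justification says that families may "select the chance to be randomized to one or both CBT or PCET-5day as a comparator". The sets are therefore PCET-I with CBT, PCET-I with PCET-5day, or all three. On method, the plan says "Randomization will be accomplished through a random number generator". It gives no allocation ratio, blocking or stratification.

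The Statistical Plan describes two ways of running the comparator analyses and gives the reason: "Because patients that agree to each randomization option may differ in unmeasured ways". The first restricts the population: "only patients that agreed to the possibility of being randomized to CBT will be included in the comparison between PCET-I and CBT". The second widens it and adds a term: "we include all patients with randomization agreement as between subject variables". The model for the treatment hypotheses is a repeated-measures ANOVA, and the only adjustment stated for it is baseline severity. The primary outcome is change in CGI-S.

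**The concern.** The first analysis is meant to be the cleaner comparison, limited to families who could have received either arm. Its entry rule for PCET-I v CBT is agreement to possible assignment to CBT. Families who accepted only CBT meet that rule, and so do families who accepted both comparators. The restriction removes one kind of mixing and leaves another inside each contrast, with no term for it.

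Randomisation takes place within the option set, so the set is a design stratum. If it predicts outcome, leaving it out puts the difference between sets into the residual variance. If the ratio of the two arms also differed between sets, arm and set would be partly confounded and the estimate would be biased.

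**Working it through.** **Which contrasts are affected.**
- PCET-I v CBT draws on the PCET-I/CBT set and the three-option set.
- PCET-I v PCET-5day draws on the PCET-I/PCET-5day set and the three-option set.
- PCET-5day v CBT can use only three-option families, so it needs no term.

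**The plan's own figure.** The Power Statement gives mid-treatment CGI-S means of 2.33 and 3.17 with SD 0.8, so the difference is 0.84. With two-sided 5% (sidedness is not stated) and 80% power, n = 2 × [0.8 × (1.960 + 0.842) / 0.84]² = 14.24. That rounds up to 15 per group, or 16 with the t distribution. The stated 14 is close enough to accept these inputs.

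**Precision under equal ratios.** The documents give the difference (0.84), the SD (0.8) and 20 per arm. I assume the following:
- half of the compared families come from each set;
- the baseline to mid-treatment correlation is 0.5, so the SD of change is 0.8 × √(2 × (1 − 0.5)) = 0.8;
- the sets differ in mean change by D = 0.5 or 1.0 points.

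With the term, SE = 0.8 × √(2/20) = 0.253, and normal-approximation power is Φ(0.84/0.253 − 1.96) = 91.3%.

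Without the term, the residual variance is multiplied by V = 1 + w(1 − w)(D/0.8)², where w is the three-option share:
- D = 0.5: V = 1 + 0.25 × 0.391 = 1.098, so SE = 0.265.
- D = 1.0: V = 1 + 0.25 × 1.563 = 1.391, so SE = 0.298.

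The power lost depends on how evenly the arms fall within each set.

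| Assumed D in change | Arms balanced within sets: Φ[(0.84 − 1.96 × SE)/0.253] | Unblocked allocation: Φ(0.84/SE − 1.96) |
|---|---|---|
| 0 | 91.3% | 91.3% |
| 0.5 | 89.7% (loss 1.6 points) | 88.7% (loss 2.6) |
| 1.0 | 84.4% (loss about 7) | 80.4% (loss 10.9) |

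If the sets differ in level by the same amount at both visits, the difference cancels in the change score. Then V = 1 and nothing is lost.

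The Participants section gives 40 per condition, not 20. At 40 per arm, SE = 0.8 × √(2/40) = 0.179 and power with the term is 99.7%. Without it, unblocked power is 99.4% (D = 0.5) or 97.8% (D = 1.0), so the precision argument largely disappears.

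**Bias.** Bias = D × [P(three-option | PCET-I) − P(three-option | CBT)].
- Equal ratios (1:1 and 1:1:1): the two probabilities are equal, so the bias is 0 for any D.
- PCET-I:CBT of 1:1 in the two-option set and 1:2 in the three-option set, w = 0.5: P(three-option | PCET-I) = (0.5 × 1/3)/(0.5 × 1/3 + 0.5 × 1/2) = 0.400. P(three-option | CBT) = (0.5 × 2/3)/(0.5 × 2/3 + 0.5 × 1/2) = 0.571. The gap is 0.171.
- With w at one third or two thirds, the same formula gives gaps of 0.150 and 0.156.

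Across these shares the bias is 0.075 to 0.086 points for D = 0.5 and 0.15 to 0.17 for D = 1.0. In round terms that is 0.08 to 0.16 points, or 10% to 19% of 0.84. Its direction depends on which set improves more. With the term, the bias is about zero. Simulation with fixed cell counts at 1:2:2 kept type I error near 5% even without the term, because the omitted difference also inflates the standard error.

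**The case against.** The strongest reply is that the plan is silent here, not wrong. Nothing in the Statistical Plan forbids an agreement term in the first analysis, and the restriction already removes the main incompatibility, namely families who could never have been assigned to CBT. The primary outcome is change, with control for baseline, so a stable difference in severity between sets does little harm. Only a difference in change matters, and the documents give no reason to expect one of 0.5 to 1.0 points. The upper value exceeds the whole 0.84 treatment effect. All of this stands and limits the size of the point. If baseline enters as a covariate and not through a change score, a pure level difference of 0.5 to 1.0 points at 1:2:2 leaves a small bias of 0.04 to 0.06.

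The second reply is that the adjusted estimate is already planned. That is partly true. In a two-arm additive PCET-I v CBT model with option set as a factor, strata containing no CBT patients add nothing to the contrast, so the second analysis would give essentially the estimate asked for here. A three-arm model could let indirect information in. For PCET-I v PCET-5day the second analysis is no substitute. Families who decline randomisation receive one of those two formats by preference, so an all-patients analysis takes in non-randomised comparisons.

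A reader might infer that the first analysis is biased as planned. The documents do not support that, because equal ratios give no bias and no section states or implies unequal ones. A reader might also argue that 40 per condition, with PCET-I in every set, forces unequal ratios. That is weak. The Abstract gives sixty children in total, the Power Statement 20 per condition and the Participants section 40, so 40 is not a settled target. Design Justification also treats additional PCET patients as an advantage and mentions no rebalancing.

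**Conclusion.** The point holds as a modest refinement. The first comparator analysis pools two strata within which families are randomised and names no term for them, while the plan itself says such families may differ and names a term for the other analysis.

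With equal ratios and about 20 per arm, the cost of omission is roughly 0 to 2 power points if the sets differ by up to 0.5 points in change, and about 5 to 10 at an extreme 1.0. It is slightly more if allocation is unblocked, and essentially nil if the sets differ only in level. A bias of about 0.08 to 0.16 points needs two conditions that the documents do not establish: sets that differ in change, and a PCET-I:CBT ratio that differs between them, taken here as 1:1 against 1:2. Set differences, set shares, ratios and the baseline correlation are all assumed. The case for the change is a small gain in precision and protection against bias, not a demonstrated flaw in the estimate.

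**What to change.** In the Statistical Plan, add to the first comparator analysis: *Option set (two or three options at randomisation) enters the PCET-I v CBT and PCET-I v PCET-5day models as a fixed factor.* Where time is a factor in the repeated-measures model, let option set interact with time, so that it adjusts change and not only level. PCET-5day v CBT needs no term. Stating the allocation ratio within each option set would also settle whether the bias can arise.

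The cost is one sentence and one degree of freedom for the factor. If the sets do not differ, the SE rises by about 1 to 2% (for example from 0.255 to 0.259, and 0.259/0.255 = 1.016). No new data are needed, because the option set must be known to randomise each family and to pay the randomisation part of the remuneration.
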